2. OBJECTIVES AND ENDPOINTS

This study will evaluate the efficacy and safety of atezolizumab in patients with NSCLC. Specific objectives and corresponding endpoints for the study are outlined in [Table 3](#).

Table 3 Objectives and Corresponding Endpoints

Objectives	Corresponding Endpoints
Primary Efficacy Objective:	

 To evaluate the efficacy of atezolizumab as neoadjuvant treatment for Stage IB, II, IIIA, and selected IIIB NSCLC 	
 Major pathologic response (defined as $\leq 10\%$ of viable tumor cells), scored by a pathologist, based on surgical resection as defined by prior studies (Hellmann et al. 2014)
Secondary Efficacy Objectives:	

 To evaluate the efficacy of atezolizumab as neoadjuvant treatment for Stage IB, II, IIIA, and selected IIIB NSCLC To evaluate response to atezolizumab in patients with PD-L1-positive vs. PD-L1-negative tumors To evaluate the association of mutational load, neoantigen score, gene expression signatures, and response to atezolizumab 	
 Pathological response in PD-L1-positive and PD-L1-negative groups Investigator-assessed response rate per RECIST v1.1 Response by: 
 Mutation load Neoantigen score Gene expression signatures
Exploratory Efficacy Objectives:	

 To evaluate the efficacy of atezolizumab as neoadjuvant or adjuvant treatment 	
 OS and, DFS
Safety Objectives:	

 To evaluate the safety and tolerability of atezolizumab as neoadjuvant or adjuvant treatment 	
 Incidence of adverse events, with severity per NCI CTCAE v4.0
Exploratory Biomarker Objectives:	

 To evaluate the immune response to atezolizumab and assess mechanisms of immune escape 	
 Assessment of immune response by flow cytometry, IHC, IF, and/or NGS, including but not limited to the characterization of T-cell subsets, NK cells, MDSC, and B cells in whole blood and tissue samples and to correlate with clinical outcome

 To investigate changes in tumor cell infiltrate in tissue samples To study the association of gene expression or mutation profiles in tumor tissue and/or blood with clinical outcome Assessment of ctDNA in blood samples obtained pre-, post-neoadjuvant therapy and throughout surveillance after surgical resection and correlation with clinical outcome measures 	
 Pathological analyses of tissue samples pre- and post-neoadjuvant therapy, at disease progression or recurrence (if available)

Table 3 Objectives and Corresponding Endpoints (cont.)

ctDNA = circulating tumor DNA; DFS = disease-free survival; IF = immunofluorescence; IHC = immunohistochemistry; NCI CTCAE v4.0 = National Cancer Institute Common Terminology Criteria for Adverse Events, version 4.0; NGS = next-generation sequencing; NK = natural killer (cells); NSCLC = non-small cell lung cancer; MDSC = myeloid-derived suppressor cell; ORR = objective response rate; OS = overall survival; PD-L1 = programmed death ligand 1; RECIST v1.1 = Response Evaluation Criteria in Solid Tumors, version 1.1; WES = whole exome sequencing.

3. STUDY DESIGN

3.1 DESCRIPTION OF THE STUDY

3.1.1 Overview of Study Design

This is a Phase II, open-label, single-arm study, designed to evaluate the efficacy of atezolizumab as a neoadjuvant therapy in patients with Stage IB, II, IIIA, or selected IIIB NSCLC scheduled for curative-intent resection by evaluating response to treatment. In addition, the safety of atezolizumab will be evaluated in this treatment setting. The study is also designed to investigate a number of laboratory correlative studies to further define the mechanism of anti-tumor activity of atezolizumab and several potential predictive biomarkers, which will help identify patients who are more likely to respond to treatment, and to aid in the design of future clinical trials. A strong correlation between PD-L1 expression and response to the anti-PD-1/PD-L1 antibodies has been demonstrated (Brahmer et al. 2010; Garon et al. 2015; Vansteenkiste et al. 2015), indicating that PD-L1 is potentially useful as a predictive biomarker. Finally, the study will also include DFS and OS as exploratory endpoints.

Approximately 180 patients with NSCLC will be enrolled in this study at approximately 15 study centers in the United States. The study will be conducted in two parts, a Neoadjuvant Atezolizumab Therapy Phase and an Adjuvant Atezolizumab Therapy Phase. During the Neoadjuvant Atezolizumab Therapy Phase, approximately 180 patients with pathologically documented Stage IB, II, IIIA, and selected IIIB NSCLC and are eligible for surgical resection with curative intent will be enrolled to receive two doses of atezolizumab as neoadjuvant therapy. Primary and secondary efficacy analyses, safety analyses, and exploratory biomarker analyses will be conducted on this cohort.

All patients who undergo surgery will enter a Surveillance period and will be monitored for disease recurrence using extended chest CT and serial blood samples for biomarker assessments for up to 2 years after surgery. Patients who do not undergo surgery will move directly to Survival Follow-up.

Patients who undergo surgery and receive adjuvant atezolizumab therapy will enter the Adjuvant Atezolizumab Therapy Phase (see Section 3.1.4). The Adjuvant Atezolizumab Therapy Phase is exploratory and will evaluate atezolizumab adjuvant therapy for up to a maximum of 12 months (up to 18 cycles) in patients who demonstrate clinical benefit

(evidence of pathologic response or absence of radiographic progression) from the Neoadjuvant Atezolizumab Therapy Phase. After surgical resection, patients may receive SOC adjuvant chemotherapy (with or without radiation) before starting atezolizumab adjuvant therapy. Any adjuvant treatment (optional SOC chemotherapy \pm radiotherapy and/or adjuvant atezolizumab) will be done concomitantly with Surveillance.

For clarity of assessments during the Surveillance period, patients will be grouped by adjuvant treatment (See [Figure 2](#) and [Appendix 2](#)):

- Subgroup A: No Adjuvant Treatment
- Subgroup B: Adjuvant Atezolizumab Treatment
- Subgroup C: SOC Chemotherapy (\pm Radiotherapy) Only
- Subgroup D: SOC Chemotherapy (\pm Radiotherapy) + Adjuvant Atezolizumab Treatment

Neoadjuvant treatment (Neoadjuvant Atezolizumab Therapy Phase) with atezolizumab 1200 mg q21d (one cycle=21 days) will be given for a maximum of 2 cycles, and adjuvant treatment (Adjuvant Atezolizumab Therapy Phase) with atezolizumab 1200 mg q21d will be given for maximum of 12 months.

Patients could be asked to consent to an optional prescreening tumor biopsy, which will then be used for tissue analysis if the patient is eligible to participate in the study based on pathologically documented NSCLC and other eligibility criteria. This prescreening consent form also includes optional collection of bronchial brushing samples and lymph node samples (see Section [4.5.8](#) and [Appendix 3](#) for details of sample collection).

[figure not shown]
Additionally, patients whose disease progresses or recurs anytime between the neoadjuvant phase and end of Surveillance period will be asked to consent to an optional tissue biopsy (tumor and lymph node, if available) at the time of progression/recurrence. Images will be collected at the time of progression and reviewed.

Patients will be closely monitored for safety and tolerability throughout the study. Safety assessments will include collection and monitoring of adverse events and laboratory abnormalities graded per the National Cancer Institute Common Terminology Criteria for Adverse Events, Version 4.0 (NCI CTCAE v4.0). Laboratory safety assessments will include the regular monitoring of hematology and blood chemistry. Tumor tissue samples, normal lung parenchyma, whole blood samples, and optional lymph node samples will be collected for biomarker assessments.

After Surveillance completion, patients will enter the Survival Follow-up period and will be followed per SOC, but information on off-protocol cancer treatment, recurrence and survival will be collected every 6 months for up to 3 years (see [Appendix 2](#)) after the patient receives the last dose of atezolizumab on study. Patients who discontinue the study due to adverse events will be followed until resolution or stabilization of the adverse event.

A schedule of activities is provided in [Appendix 1](#).

[figure not shown]
Figure 1 Study Schema

CT = computed tomography; MRI = magnetic resonance imaging; PET = positron emission tomography; PFT = pulmonary function test; SOC = standard of care.

^a Refer to [Appendix 2](#).

Figure 2 Surveillance Flow Chart with Treatment Subgroups

^a Total Surveillance period =2 years. If patient discontinues treatment for any reason, they should remain in Surveillance until they complete 2 years and then move to Survival Follow-up.

3.1.2 Neoadjuvant Atezolizumab Therapy Phase

During this phase of the study, patients will have their NSCLC assessed by CT scan of the chest (with IV contrast), PET/CT, and brain MRI (preferably with gadolinium). The CT and PET CT images will be collected and reviewed for further analyses. Brain imaging may be omitted for patients with clinical Stage IB tumors but should be obtained for patients with clinical Stages II, IIIA, and selected IIIB tumors. If brain MRI is not feasible for technical or patient-related reasons (e.g., pacemaker, severe claustrophobia), brain CT scan with IV contrast should be obtained. Tumor biopsy, whole blood samples, optional lymph node samples and optional bronchial brushings will be obtained before treatment with atezolizumab. Either archival or newly collected sections of tumor biopsy will be formalin-fixed and fresh frozen (see Section 4.1.1). Optional lymph nodes will be sectioned for preparation in media and formalin-fixed.

Pretreatment whole blood will be used for IMMUNOME, and processed for plasma, serum, normal control DNA, and peripheral blood mononuclear cells (PBMC) for correlative studies.

Patients will receive two doses of atezolizumab administered 3 weeks apart before surgical resection. Patients who have radiologic progression prior to the second dose will be discontinued from atezolizumab and the patient will not have surgical resection as part of this study.

Surgical Resection

Following induction therapy in the Neoadjuvant Atezolizumab Therapy Phase, patients will undergo surgical resection of the primary tumor and associated lymph nodes.

Repeat chest CT scan, PET/CT scan, and MRI of the brain will be obtained prior to surgical resection and collected for review.

Resection may be accomplished via an open or minimally invasive procedure (i.e., thoracotomy, sternotomy, clamshell or hemiclamshell incisions; or video assisted thoracic surgery (VATS) or robotically assisted VATS.

Pathologic complete resection of the primary tumor (R0) should be performed. Anatomic resection via segmentectomy, lobectomy, bilobectomy or pneumonectomy is strongly preferred although wedge resection is acceptable for very small (2 cm or less) tumors located peripherally where wedge resection permits a wide margin (at least 1 cm in all directions).

Hilar and mediastinal lymph node dissection or sampling should be performed. For right sided resections, this involves at least lymph nodes from levels 4R, 7, 10R, and 11R. For left sided resections, this involves at least lymph nodes from levels 5/6, 7, 10L, and 11L. Patients in whom a complete resection is not achieved will be discontinued from the study and will be replaced.

Pathologic specimens will undergo standard histopathologic and immunohistochemical evaluation for lung cancer. Tumor, normal lung parenchyma, and draining lymph nodes will be harvested immediately after resection. Sections of tumor will be fresh frozen and formalin-fixed for correlative studies (see [Appendix 3](#)). Sections of lymph nodes will be freshly prepared in media and formalin-fixed for correlative studies. Sections of adjacent normal lung tissue will be formalin-fixed for correlative studies. Sections of tumor, adjacent normal lung tissue and lymph node may be freshly dissociated for correlative studies.

Whole blood samples will be collected at the time of surgical resection for correlative studies. The blood will be used for IMMUNOME and processed for PBMC, plasma, and serum for correlative studies.

At the postoperative follow-up visit, patients whose tumors have not demonstrated evidence of pathologic response or who have radiographic progression will have an end-of-study treatment (atezolizumab) visit, after which they will enter Surveillance for 2 years then Survival Follow-up for 1 year.

Whole blood will be collected at postoperative follow-up visit and will be processed for plasma, serum, and PBMC for correlative studies.

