3.1.3 Surveillance

All patients who undergo surgery will enter the Surveillance Period. During Surveillance, patients will be monitored by extended chest CT scans (including liver and adrenals). Whole blood will be collected for plasma and serum, and PBMCs (at selected timepoints), every 6 weeks to 3 months for 2 years for correlative studies (see [Appendix 2](#) for details). Upon completion of Surveillance, patients enter Survival Follow-up. Patients whose disease progresses or recurs during Surveillance will discontinue from Surveillance and enter Survival Follow-up.

For patients previously enrolled under Protocol Version 3 or earlier:

- If the patient re-consents under Protocol Version 4 >3 months after the Post-surgery Visit: patient will not enter Surveillance and will follow the schedule of activities from Protocol Version 3 (see [Appendix 11](#)).
- If the patient re-consents under Protocol Version 4 at any time between Screening and the Post-surgery Visit: patient will be offered to enter Surveillance and follow Protocol Version 4 schedule of activities.
- If the patient re-consents under Protocol Version 4 ≤ 3 months after the Post-surgery Visit: patient will be offered to enter Surveillance and follow Protocol Version 4 schedule of activities only if post-surgery baseline chest CT scan is available. If chest CT scan is not available, patient will follow the schedule of activities from Protocol Version 3 (see [Appendix 11](#)).

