3.1.4 Adjuvant Atezolizumab Therapy Phase

Patients whose tumors have evidence of pathologic response or lack of radiographic progression will be eligible for the Adjuvant Atezolizumab Therapy Phase, which will occur during the Surveillance period.

During this part of the study, patients will receive adjuvant atezolizumab for up to a maximum of 12 additional months (up to 18 cycles). Adjuvant atezolizumab treatment may be started directly after surgery or after adjuvant SOC chemotherapy (with or without radiation). Choice of adjuvant SOC chemotherapy will be at the discretion of the treating physician, depending on the disease stage, as deemed clinically appropriate. It is highly recommended that any adjuvant treatment be initiated within 120 days after surgery. Additionally, it is recommended that patients who receive SOC Chemotherapy (\pm Radiotherapy) initiate adjuvant atezolizumab within 60 days of SOC Chemotherapy \pm Radiotherapy (whichever occurs last). If adjuvant treatment is planned to start outside of the recommended window, *Investigators may discuss it with the Medical Monitor.*

Whole blood samples will be collected prior to infusion on adjuvant Cycle 1, Day 1. Subsequent blood samples will be collected during Surveillance (see Section 3.1.3) and 30 days after the last dose for correlative studies. The blood will be processed for PBMC, plasma, and serum.

Optional bronchial brushings samples may be collected from patients undergoing bronchoscopy or EBUS at prescreening or screening and approximately 3–4 months after starting adjuvant atezolizumab treatment (Group D only).

For all patients whose disease progresses or recurs (confirmed by imaging) at any time between neoadjuvant treatment and surveillance may undergo an optional tissue biopsy (tumor and lymph node, if available) for correlative studies, which will require a separate ICF signature (see Section 4.5.1). A blood sample will also be collected at the time of disease progression/recurrence.

All patients will enter Survival Follow-up, which will cover new anti-cancer treatment, DFS, and OS for up to 3 years after the last dose of atezolizumab (See [Appendix 2](#) for details regarding time in Survival Follow-up).

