4.6 PATIENT, TREATMENT, STUDY, AND SITE DISCONTINUATION

4.6.1 Patient Discontinuation

Patients have the right to voluntarily withdraw from the study at any time for any reason. In addition, the investigator has the right to withdraw a patient from the study at any time. Reasons for withdrawal from the study may include, but are not limited to, the following:

- Patient withdrawal of consent at any time
- Any medical condition that the investigator or Sponsor determines may jeopardize the patient's safety if he or she continues in the study
- Investigator or Sponsor determines it is in the best interest of the patient
- Patient non-compliance

Every effort should be made to obtain information on patients who withdraw from the study but do not withdraw consent. The primary reason for withdrawal from the study should be documented on the appropriate eCRF. However, patients will not be followed for any reason after consent has been withdrawn. Patients who withdraw from the study will not be replaced.

If a patient withdraws from the study, the study staff may use a public information source (e.g., county records) to obtain information about survival status.

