Baseline Extended Chest CT scan and associated blood sample collection should ideally be obtained at the post-surgery visit/surveillance baseline (4–6 weeks after surgery). However, if it is not possible to perform the assessments at the post-surgery visit/surveillance baseline it is also acceptable to have them obtained at S1 (approximately 6 weeks after post-surgery visit/surveillance baseline). In this case:

- Baseline Chest CT Scan and blood sample collection for PBMC will be obtained at S1
- The next scans will be obtained at S3 and then approximately every 3 months up to S9 (if baseline scan is obtained at S1 then S2 scan does not need to be obtained)

* Whole blood sample for PBMC needs to be collected at S1 instead of S2 (on the same visit when the scans are performed). .

Appendix 2
Timing of Surveillance Assessments (cont.)

Table 1 Group A – No Adjuvant Treatment

Post-Surgery Visit / Surveillance Baseline	S1 Visit	S2 Visit	Surveillance Assessments during SOC Chemotherapy	Surveillance Assessments during Adjuvant Atezolizumab	Assessments during Surveillance Only (S3 to S9)	Time in Survival Follow-Up ^a
(4-6 weeks after surgery)	6 weeks after Surveillance baseline (\pm 7days)	6 weeks after S1 Visit (\pm 7days)	N/A	N/A	See Below for Timing	–
Baseline extended chest CT scan and blood sample for biomarker analysis	Blood sample for biomarker analysis	Extended chest CT scan and blood sample for biomarker analysis	N/A	N/A	Extended chest CT scan and blood sample collection for biomarker analysis At approximately every 3 months after S2 for 2 years (S3 to S9).	1 year

EBUS=Endobronchial ultrasound; SOC=standard of care; S=Surveillance (visit).

Notes: If visit is outside of the recommended window, please contact Medical Monitor for guidance and approval; if visit is outside of window, all indicated procedures should still be performed. Patients whose disease progresses or recurs during Surveillance will discontinue from Surveillance and enter Survival Follow-up.

^a If patient discontinues surveillance for any reason, patient will still be followed up for 3 years after last dose of atezolizumab treatment.

Appendix 2

Timing of Surveillance Assessments (cont.)

Table 2 Group B – Adjuvant Atezolizumab Treatment

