### 6.3.3 Exploratory Analysis

Overall survival (OS) will be analyzed in efficacy population. OS is defined as the time from the date of first dose until the date of death from any cause. This is the length of time from the start of treatment that patients are still alive. Subjects alive at the end of the study or lost to follow-up will be censored on the date of last follow-up disease assessment.

Disease-free survival (DFS) will be analyzed in primary efficacy population. DFS is defined as the time from the first date of no disease (i.e., date of surgery with complete resection) to local or distant recurrence or death due to any cause, whichever occurs first. DFS will be analyzed only for patients who underwent surgery with complete resection. After surgery with complete resection, data for patients who withdraw from the study without disease recurrence or death will be censored at the date of last disease follow-up assessment. Patients without post-surgery disease follow-up assessments but known to be alive will be censored at the date of surgery with complete resection plus one day.

Event-free survival (EFS) will be analyzed in efficacy population. EFS is defined as the time from the date of first dose to any of the following events, whichever occurs first:

- Progression of disease per RECIST v1.1 that precludes surgery with complete resection
- Local or distant disease recurrence
- Death due to any cause

Patients who have not experienced disease progression that precludes surgery with complete resection, local or distant disease recurrence, or death at the time of analysis will be censored at the time of last tumor or disease follow-up assessment. Patients with no post-baseline tumor or disease follow-up assessment but known to be alive will be censored at the date of first dose plus one day.

The durations of overall survival, disease-free survival and event-free survival will be computed in months as:

$$\frac{(End\ Date - Start\ Date + 1)}{(365.25/12)}$$

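### Patients without complete resection: the protocol both drops them and follows them, and the SAP's EFS event list does not cover them, so exploratory OS and EFS could be biased upward

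*Protocol*

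**What the plan says.** **Leaving the study.** Protocol 3.1.2, under Surgical Resection, and the matching synopsis text: "Patients in whom a complete resection is not achieved will be discontinued from the study and will be replaced".

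**Staying in follow-up.** Protocol 3.1.3: "All patients who undergo surgery will enter the Surveillance Period". The synopsis, 3.1.1 and Appendix 1 footnote h say the same, with no exception for incomplete resection. Protocol 3.1.4: "All patients will enter Survival Follow-up, which will cover new anti-cancer treatment, DFS, and OS for up to 3 years" after the last dose. Appendix 2, Table 1 footnote a: "If patient discontinues surveillance for any reason, patient will still be followed up for 3 years after last dose of atezolizumab treatment". On study withdrawal, 4.6.1 says: "Every effort should be made to obtain information on patients who withdraw from the study but do not withdraw consent". It adds that "the study staff may use a public information source (e.g., county records) to obtain information about survival status".

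**Analysis.** SAP Section 5 defines the efficacy population by at least one dose and no EGFR or ALK mutant tumor, with no condition on resection. SAP 6.3.3: "Overall survival (OS) will be analyzed in efficacy population". EFS uses the same population. The EFS events are "Progression of disease per RECIST v1.1 that precludes surgery with complete resection", local or distant recurrence, and death from any cause. Patients without an event are censored for EFS at the last tumor or disease follow-up assessment. For OS, patients alive at study end or lost to follow-up are censored at the last follow-up disease assessment. DFS and the primary analysis exclude incomplete resections.

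**The concern.** The first instruction removes a group from observation while the analysis keeps that group in the denominator. Kaplan-Meier then gives these patients the later experience of those still under observation, who are mostly patients with complete resection. If residual disease carries a worse outlook, censoring is informative and the OS and EFS curves are too high.

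The EFS definition has its own gap. Complete resection is the benchmark in the first event, yet surgery that fails to achieve it is not an event unless RECIST progression came first. Later growth of residual disease fits poorly under recurrence, because the SAP's DFS text dates freedom from disease from a complete resection, which these patients never had. So even with full follow-up, death is the only event that certainly counts for them after surgery.

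At stake are the six-monthly OS and EFS rates to 36 months and the log-rank comparisons by pathologic response and PD-L1 status. The OS and EFS tables are flagged in SAP Table 3 for both the efficacy interim and the primary analysis.

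**Working it through.** The documents give no OS or EFS figure, event target or incomplete-resection rate, so there is no plan figure to reproduce. The check covers the follow-up rules, the censoring date, and the size under stated assumptions.

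**1. Do the follow-up rules conflict?** Yes. The sentence in 3.1.2 cannot easily be read as stopping study drug only. Later in the same section, patients without pathologic response have an end-of-treatment visit and then enter Surveillance, so the protocol separates ending treatment from leaving the study. The provisions that might rescue the data do not clearly apply:
- 4.6.1 concerns patients who withdraw and says they are not replaced, whereas incomplete-resection patients are replaced. Its public-records search is optional.
- The Appendix 2 footnote concerns leaving Surveillance, not leaving the study.

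**2. When would censoring fall?** Appendix 1 puts the pre-surgery visit at Day 36, surgery at Day 40 (±10) and the post-surgery visit 4 to 6 weeks later, nominally Day 68 to 82. With 365.25/12 = 30.44 days per month, the last assessment falls between 36/30.44 = 1.2 and 82/30.44 = 2.7 months. That is near surgery, but not at surgery by rule.

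**3. Size at 24 months, EFS.** Assumptions, none from the documents: 10% of patients unresected and counted as events by the time of surgery; surgery at 1.3 months; exponential times from surgery; median EFS 36 months after complete and 10 months after incomplete resection; share q with incomplete resection.
- Complete: 2^(−22.7/36) = 0.646. Incomplete: 2^(−22.7/10) = 0.207.
- Censored near surgery: 0.90 × 0.646 = 0.581.
- Followed, q = 10%: 0.80 × 0.646 + 0.10 × 0.207 = 0.538.
- Bias = q × (0.646 − 0.207) = q × 0.439, which is 1.3, 2.2 and 4.4 points at q = 3, 5 and 10%.

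**4. Size at 36 months, OS or EFS.** Let S be the 36-month rate in the other patients and HR the hazard ratio for incomplete resection, both assumed. Early censoring gives S. Full follow-up gives (1 − q)S + q·S^HR. The bias is q(S − S^HR).

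| S | HR | S − S^HR | q = 3% | q = 5% | q = 10% |
|---|---|---|---|---|---|
| 0.60 | 2 | 0.240 | 0.7 | 1.2 | 2.4 |
| 0.60 | 3 | 0.384 | 1.2 | 1.9 | 3.8 |
| 0.80 | 2 | 0.160 | 0.5 | 0.8 | 1.6 |
| 0.80 | 3 | 0.288 | 0.9 | 1.4 | 2.9 |

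Entries are percentage points. At HR = 1 the bias is zero. A simulation with 180 patients, 3,000 runs and censoring at Day 36 gives 0.8 to 1.8 points at q = 5% and 1.6 to 3.6 at q = 10%.

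**5. The definition gap, kept separate.** Counting incomplete resection as an EFS event at surgery gives 0.80 × 0.646 = 0.517 at 24 months for q = 10%. The distance from 0.581 is q × 0.646, about 2, 3 and 6 points at q = 3, 5 and 10%. This difference includes a change of endpoint definition and is not an estimate of censoring bias.

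**The case against.** The strongest reply is that loss of follow-up is only one of two readings. Most of the protocol keeps these patients: 3.1.1, 3.1.3, 3.1.4, 3.2, the follow-up text in 4.5.6 and Appendix 1. Section 4.6.1 asks for every effort to obtain data after withdrawal. Applied that way, OS has no bias from this source. This stands, and it makes the bias conditional. It does not remove the conflict, because a site that follows 3.1.2 as written would stop contact.

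Three stronger readings are tempting and are not supported:
- A reader might infer that these patients can have no EFS event. Death counts, observed recurrence counts, and so does RECIST progression that precluded complete resection.
- A reader might infer that they are censored at surgery. The SAP uses the last tumor or disease assessment for EFS and the last follow-up disease assessment for OS.
- A reader might take the 2, 3 and 6 points in step 5 as the bias. They compare two EFS definitions; only the smaller figures estimate the effect of censoring.

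Scale also matters. With 180 patients and a rate near 55%, the binomial standard error is √(0.55 × 0.45/180) = 3.7 points, so a shift of 1 to 2 points is about half a standard error or less. The endpoints are exploratory in a single-arm study with no alpha or power attached. That limits the priority. But the bias has a known direction if prognosis is worse, more patients would not reduce it, and it is cheap to prevent.

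**Conclusion.** The point holds in a conditional form. The protocol contradicts itself on whether patients without complete resection remain under observation, and the SAP keeps them in the OS and EFS population. If 3.1.2 is applied literally, no later data are retrieved and their prognosis is worse, OS and EFS are biased upward by about 1 to 4 points at assumed incomplete-resection rates of 3 to 10% (computed range 0.5 to 4.4). If the follow-up sections are applied, the OS bias is about zero and only the EFS event gap remains. The rates, medians and hazard ratios are all assumptions.

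The documents do not support saying outright that OS and EFS are overstated. Nor does the problem reach the primary test through this route, since the primary efficacy population already excludes incomplete resections.

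**What to change.** **Protocol.** Reconcile the replacement sentence in 3.1.2 and the synopsis with 3.1.1, 3.1.3, 3.1.4 and Appendix 1. Patients without complete resection, even if replaced for the primary analysis, should stay in survival and recurrence follow-up for up to 3 years after the last dose. The text should also say whether they have the Surveillance assessments. This concerns data collection only and proposes no change to treatment.

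**SAP 6.3.3.** Count progression of residual disease after incomplete resection as an EFS event, dated at the assessment that shows it. Report a sensitivity analysis that counts surgery without complete resection as an EFS event on the date of surgery. State that a survival contact counts toward the OS censoring date; as written, a patient reached only for vital status gains no time at risk.

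**Cost.** Continued follow-up of a few patients (3 to 10% of 180 is about 5 to 18), any Surveillance assessments the sponsor retains for them, a short SAP change and one extra analysis. The EFS estimate becomes slightly less favourable.
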